APPENDIX E. QUALITY OF LIFE QUESTIONNAIRE (ENGLISH)

EORTC QLQ-C30 (version 3)

We are interested in some things about you and your health. Please answer all of the questions yourself by circling the number that best applies to you. There are no "right" or "wrong" answers. The information that you provide will remain strictly confidential.

Patient Study #: _____

Please fill in your initials: _____

Your birthdate (Day, Month, Year): _____

Today's date (Day, Month, Year): _____

	Not at All	A Little	Quite a Bit	Very Much
1. Do you have any trouble doing strenuous activities, like carrying a heavy shopping bag or a suitcase?	1	2	3	4
2. Do you have any trouble taking a long walk?	1	2	3	4
3. Do you have any trouble taking a short walk outside of the house?	1	2	3	4
4. Do you need to stay in bed or a chair during the day?	1	2	3	4
5. Do you need help with eating, dressing, washing yourself or using the toilet?	1	2	3	4
During the past week:		Not at All	A Little	Quite a Bit
6. Were you limited in doing either your work or other daily activities?	1	2	3	4
7. Were you limited in pursuing your hobbies or other leisure time activities?	1	2	3	4
8. Were you short of breath?	1	2	3	4
9. Have you had pain?	1	2	3	4
10. Did you need to rest?	1	2	3	4
11. Have you had trouble sleeping?	1	2	3	4
12. Have you felt weak?	1	2	3	4
13. Have you lacked appetite?	1	2	3	4
14. Have you felt nauseated?	1	2	3	4
15. Have you vomited?	1	2	3	4
16. Have you been constipated?	1	2	3	4

Please go on to the next page

During the past week:	Not at All	A Little	Quite a Bit	Very Much
17. Have you had diarrhea?	1	2	3	4
18. Were you tired?	1	2	3	4
19. Did pain interfere with your daily activities?	1	2	3	4
20. Have you had difficulty in concentrating on things, like reading a newspaper or watching television?	1	2	3	4
21. Did you feel tense?	1	2	3	4
22. Did you worry?	1	2	3	4
23. Did you feel irritable?	1	2	3	4
24. Did you feel depressed?	1	2	3	4
25. Have you had difficulty remembering things?	1	2	3	4
26. Has your physical condition or medical treatment interfered with your family life?	1	2	3	4
27. Has your physical condition or medical treatment interfered with your social activities?	1	2	3	4
28. Has your physical condition or medical treatment caused you financial difficulties?	1	2	3	4

For the following questions please circle the number between 1 and 7 that best applies to you

29. How would you rate your overall health during the past week?

1 2 3 4 5 6 7

30. How would you rate your overall quality of life during the past week?

1 2 3 4 5 6 7

**APPENDIX F. EORTC QLQ – EN24**

Patients sometimes report that they have the following symptoms or problems. Please indicate the extent to which you have experienced these symptoms or problems.

During the past week:	Not at all	A little	Quite a bit	Very much
1. Have you had swelling in one or both legs?	1	2	3	4
2. Have you felt heaviness in one or both legs?	1	2	3	4
3. Have you had pain in your lower back and / or pelvis?	1	2	3	4
4. When you felt the urge to pass urine, did you have to hurry to get to the toilet?	1	2	3	4
5. Have you passed urine frequently?	1	2	3	4
6. Have you had leaking of urine?	1	2	3	4
7. Have you had pain or a burning feeling when passing urine?	1	2	3	4
8. When you felt the urge to move your bowels, did you have to hurry to get to the toilet?	1	2	3	4
9. Have you had any leakage of stools?	1	2	3	4
10. Have you been troubled by passing wind?	1	2	3	4
11. Have you had cramps in your abdomen?	1	2	3	4
12. Have you had a bloated feeling in your abdomen?	1	2	3	4
13. Have you had tingling or numbness in your hands or feet?	1	2	3	4
14. Have you had aches or pains in your muscles or joints?	1	2	3	4
15. Have you lost hair?	1	2	3	4
16. Has food and drink tasted differently from usual?	1	2	3	4

During the past week:

	Not at all	A little	Quite a bit	Very much
--	-------------------	-----------------	--------------------	------------------

17. Have you felt physically less attractive as a result of your disease or treatment? 1 2 3 4

18. Have you felt less feminine as a result of your disease or 1 2 3 4

During the past 4 weeks:

	Not at all	A little	Quite a bit	Very much
--	-------------------	-----------------	--------------------	------------------

19. To what extent were you interested in sex? 1 2 3 4

20. To what extent were you sexually active? 1 2 3 4

Answer these questions only if you have been sexually active during the past 4 weeks:

21. Has your vagina felt dry during sexual activity? 1 2 3 4

22. Has your vagina felt short and / or tight? 1 2 3 4

23. Have you had pain during sexual intercourse or other sexual activity? 1 2 3 4

24. Was sexual activity enjoyable for you? 1 2 3 4

Appendix G EORTC QLQ-C30 Spanish Version

SPANISH (US)

EORTC QLQ-C30 (versión 3)

Estamos interesados en algunas cosas sobre usted y su salud. Por favor, conteste todas las preguntas usted mismo/a marcando un círculo el número que mejor se aplique a su caso. No hay respuestas “correctas” ni “incorrectas”. La información que nos proporcione se mantendrá estrictamente confidencial.

Por favor, escriba sus iniciales:

Su fecha de nacimiento (día, mes, año):

La fecha de hoy (día, mes, año):

31 _____

	Para nada	Un poco	Bastante	Extremada- mente
1. ¿Tiene alguna dificultad para realizar actividades que requieran un gran esfuerzo como llevar una bolsa de compras pesada o una maleta?	1	2	3	4
2. ¿Tiene alguna dificultad para salir a caminar por largo tiempo?	1	2	3	4
3. ¿Tiene alguna dificultad para salir a caminar por  corto tiempo fuera de la casa?	1	2	3	4
4. ¿Necesita quedarse en cama o en una silla durante el día?	1	2	3	4
5. ¿Necesita ayuda para comer, vestirse, bañarse o ir al baño?	1	2	3	4

Durante la última semana:

	Para nada	Un poco	Bastante	Extremada- mente
6. ¿Estuvo limitado/a al hacer su trabajo u otras actividades diarias?	1	2	3	4
7. ¿Estuvo limitado/a al hacer sus pasatiempos u otras actividades de tiempo libre?	1	2	3	4
8. ¿Le faltó el aire?	1	2	3	4
9. ¿Ha tenido dolor?	1	2	3	4
10. ¿Necesitó descansar?	1	2	3	4
11. ¿Ha tenido problemas para dormir?	1	2	3	4
12. ¿Se ha sentido débil?	1	2	3	4
13. ¿Le ha faltado el apetito?	1	2	3	4
14. ¿Ha sentido náuseas?	1	2	3	4
15. ¿Ha vomitado?	1	2	3	4
16. ¿Ha estado estreñido/a?	1	2	3	4

Por favor, continúe en la página siguiente

Durante la última semana:	Para nada	Un poco	Bastante	Extremada- mente
			SPANISH (US)	
17. ¿Ha tenido diarrea?	1	2	3	4
18. ¿Estuvo cansado/a?	1	2	3	4
19. ¿Interfirió el dolor en sus actividades diarias?	1	2	3	4
20. ¿Ha tenido dificultad para concentrarse en cosas como leer el periódico o ver televisión?	1	2	3	4
21. ¿Se sintió tenso/a?	1	2	3	4
22. ¿Se preocupó?	1	2	3	4
23. ¿Se sintió irritable (enojado/a)?	1	2	3	4
24. ¿Se sintió deprimido/a?	1	2	3	4
25. ¿Ha tenido dificultad para recordar cosas?	1	2	3	4
26. ¿Ha interferido su condición física o su tratamiento médico en su vida familiar?	1	2	3	4
27. ¿Ha interferido su condición física o su tratamiento médico en sus actividades sociales?	1	2	3	4
28. ¿Le ha causado su condición física o su tratamiento médico dificultades económicas?	1	2	3	4

Para las siguientes preguntas, por favor, marque con un círculo el número del 1 al 7 que mejor se aplique a su caso

29. ¿Cómo calificaría su salud en general durante la última semana?

1 2 3 4 5 6 7

Excelente

30. ¿Cómo calificaría su calidad de vida en general durante la última semana?

1 2 3 4 5 6 7

Excelente

Appendix H EORTC QLQ –EN24 Spanish Translation

SPANISH (US)

**EORTC QLQ – EN24**

Las pacientes a veces dicen que tienen los siguientes síntomas o problemas. Por favor, indique hasta qué punto ha experimentado estos síntomas o problemas.

Durante la última semana:

		Para nada	Un poco	Bastante	Muchí- simó
1.	¿Tuvo hinchazón en una o ambas piernas?	1	2	3	4
2.	¿Sintió pesadez en una o ambas piernas?	1	2	3	4
3.	¿Tuvo dolor en la parte baja de la espalda y/o en la pelvis?	1	2	3	4
4.	Cuando sintió la necesidad urgente de orinar, ¿tuvo que ir de prisa al baño?	1	2	3	4
5.	¿Orinó con frecuencia?	1	2	3	4
6.	¿Tuvo pérdidas de orina involuntarias?	1	2	3	4
7.	¿Tuvo dolor o ardor al orinar?	1	2	3	4
8.	Cuando sintió la necesidad urgente de defecar, ¿tuvo que ir de prisa al baño?	1	2	3	4
9.	¿Tuvo pérdidas de heces involuntarias?	1	2	3	4
10.	¿Se sintió molesta por haber tenido flatulencia (expulsar gases)?	1	2	3	4
11.	¿Sintió retortijones (cólicos) en el abdomen?	1	2	3	4
12.	¿Tuvo sensación de hinchazón en el abdomen?	1	2	3	4
13.	¿Sintió hormigueos o adormecimiento en las manos o en los pies?	1	2	3	4
14.	¿Sintió dolores o molestias en los músculos o articulaciones (coyunturas)?	1	2	3	4
15.	¿Se le cayó algo de pelo?	1	2	3	4
16.	¿Sintió que el sabor de la comida y la bebida es diferente de lo normal?	1	2	3	4

Por favor, continúe en la página siguiente

SPANISH (US)

Durante la última semana:

		Para nada	Un poco	Bastante	Muchí- simo
17.	¿Se sintió menos atractiva físicamente a consecuencia de su enfermedad o tratamiento?	1	2	3	4
18.	¿Se sintió menos femenina como consecuencia de su enfermedad o tratamiento?	1	2	3	4

Durante las últimas 4 semanas:

		Para nada	Un poco	Bastante	Muchí- simo
19.	¿Hasta qué punto estuvo interesada en actividad sexual?	1	2	3	4
20.	¿Hasta qué punto tuvo una vida sexual activa?	1	2	3	4

Conteste las siguientes preguntas solo si usted estuvo activa sexualmente durante las últimas 4 semanas:

21.	¿Sintió sequedad vaginal durante la actividad sexual?	1	2	3	4
22.	¿Sintió la vagina acortada y/o estrecha?	1	2	3	4
23.	¿Tuvo dolor durante el coito u otra actividad sexual?	1	2	3	4
24.	¿Le resultó placentera la actividad sexual?	1	2	3	4

Protocol name: Short Course Adjuvant Vaginal Brachytherapy in Early Endometrial Cancer Compared to Standard of Care

Version Date: 18JUN2025

Principal Investigator: [name]

APPENDIX I. Health Care Expense Survey

Health Care Expense Survey

Patient Study ID: _____

Patient Initials: _____

Date of Completion: _____ / _____ / _____

Health Care Expense Survey

Before you were diagnosed with endometrial cancer, did you do paid or unpaid work outside the home?

Yes No

If you worked outside the home, which of the following best applies to you?

Paid work outside the home Yes No

Unpaid work outside the home Yes No (including work in a family farm or business).

Self-employed / business owner Yes No

If you worked outside the home:

How many days per week did you work? ____ (days)

How many hours per day did you work? ____ (hours)

What is your profession?

In what industry do you work?

What is / was your job title?

NOTE: This section is designed to capture the out of pocket expenses associated with radiation therapy.

How many hours were spent in total for each radiation treatment (time from leaving home/other accommodation or work to return to home/other accommodation or work)?

____ (hours)

What is the distance from the radiation treatment facility from home/other accommodation or work? ____ (miles)

Did you commute daily to radiation treatment from your home? Yes No

(If yes), method of transport used to get to the radiation therapy facility (Check all that apply)

Car Yes No

(If yes) approximate cost for parking per visit \$_____.____

Did you drive yourself? Yes No

Were you driven? Yes No

Was it a combination of driving yourself or being driven Yes No

Shuttle Yes No

(If yes) Approximate cost per visit \$_____.____

Public transport Yes No

(If yes) Approximate cost per visit \$_____.____

On foot Yes No

Taxi/car service Yes No

(If yes) Approximate cost per visit (both ways) \$_____.____

(If no), which of the follow apply (check one):

I was in a health care facility during radiation

I was living with a friend/family member during radiation (answer the commuting questions above)

I stayed hotel, apartment, or similar facility during radiation (answer the commuting questions above)

If hotel, apartment or similar facility, estimated cost of lodging during your radiation treatment \$_____.____

Number of radiation treatments during which at least one other person accompanied patient ____

Number of visits to radiation treatment facility since completing radiation therapy (follow up visits) ____

From the 1st day of starting radiation, until 40 days after the completion of radiation:

Number of days the patient was unable to go to work at all ____

Number of days the patient went to work part-time ____

If part time, number of hours reduced from typical work day ____

Estimate child care costs due to radiation therapy \$____, ____

Estimate wages lost due to radiation therapy \$____, ____

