2 COHORT 2 (PILOT EXPANSION)

2.1 Primary Objective and Endpoint

2.1.1 The primary objective is to evaluate the frequency and severity of patient-reported financial toxicity in patients with early-stage endometrial cancer treated with vaginal cuff-brachytherapy (VCB) at one-month post-VCB.

ENDPOINT:

Patient-reported financial toxicity will be assessed through the Functional Assessment of Chronic Illness Therapy (FACIT)-Cost questionnaire, administered at 1 month post-brachytherapy

2.2 Exploratory Objectives:

2.2.1 Exploratory objectives will include evaluation of differences in patient-reported financial toxicity between cohorts, to assess any impact of treatment duration on outcomes.

ENDPOINT:

Mean scores for each individual measure will be reported and compared between the two arms enrolled in Cohort 2.

Using a COST < 26 as a cutoff for moderate financial distress, the proportion of patients experiencing moderate distress in each cohort will be reported and compared.

2.2.2 Exploratory objectives include evaluation of patient-reported diet and physical activity levels and quality of life in patients with early-stage endometrial cancer treated with vaginal cuff-brachytherapy (VCB) at one-month post-VCB.

ENDPOINT:

Patient-reported diet and physical activity levels will be assessed through the Health Care Expense Survey, NCI Diet History Questionnaire III (DHQ-3), and

Physical Activity Questionnaire (ACT24) administered at 1 month post-brachytherapy.

Quality-of-life will be assessed through to Evaluate responses to the QLQ30 Questionnaire, EN24 Questionnaire in the patient population.

Mean scores from FACIT-COST with be correlated with QLQ30 scores

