6 TREATMENT PLAN

6.1 Administration Schedule

Experimental arm: 11Gy will be prescribed to the surface with a minimal treatment length of 3 cm. Two fractions will be given, one week apart. For this instance a week apart indicates an intervening weekend between treatments. Ideally treatments would be 7 days apart. Inspection of the vaginal cuff is required to ensure there is no dehiscence. Dose should be optimized to the cylinder as seen in Figure 1, Appendix D, with dose normalized to 100% at the tip and at the midpoint of the active length. Dose at $\frac{1}{2}$ cm will be recorded also. In cases of fulminant LSVI, the entire vagina may be treated per physician discretion. In most scenarios, the maximal treatment length should not exceed 5 cm. CT simulation shall be performed.

Control arm: One of the following fractions schemes are permitted based on the decision of the treating physician:

- 7 Gy at $\frac{1}{2}$ cm x 3 fractions over no more than three weeks.
- 5-5.5 Gy at $\frac{1}{2}$ cm x 4 fractions over no more than three weeks.
- 6 Gy at the surface of the cylinder x 5 fractions over no more than three weeks.

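### Appendix I's commuting question presumes daily visits, so a woman who travelled from home on a non-daily schedule has no route to the travel-cost items

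*Combined protocol and SAP*

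**What the plan says.** The expense survey in Appendix I states that its treatment section is meant to record out-of-pocket spending linked to radiation. Two items come first and go to every respondent: hours spent per treatment, and distance to the facility. The next question is "Did you commute daily to radiation treatment from your home", answered yes or no.

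- **Yes** leads to the "method of transport used to get to the radiation therapy facility" and, within that block, to parking, shuttle, public-transport and taxi costs per visit.
- **No** leads to a list introduced by "If no), which of the follow apply (check one". It has three entries. The first is "I was in a health care facility during radiation". The second begins "I was living with a friend/family member during radiation (answer the commuting questions above". The third covers a hotel, apartment or similar, and carries the same instruction to go back to the commuting items.

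Section 6.1 sets the schedules. For the experimental arm, "Two fractions will be given, one week apart", with a weekend in between. The control arm receives 3, 4 or 5 fractions at the treating physician's choice, within three weeks and with no fixed interval.

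Section 2.2.2 states that "Patient-reported diet and physical activity levels will be assessed through the Health Care Expense Survey", together with the diet and activity questionnaires. The Cohort 2 primary endpoint is FACIT-COST (sections 2.1.1 and 10.2.3). Exploratory endpoints are summarised descriptively without testing (section 10.2.5).

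**The concern.** The question combines two things: where the patient slept, and how often she travelled. The follow-up after a no answer assumes that no means she stayed somewhere other than home. In this trial that does not follow. A woman who drives in from home once a week is correct to answer no, because she did not commute daily. She then meets a check-one list on which no entry is true of her, and no instruction to complete the transport and cost items.

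What is at stake is the per-visit spending of patients living at home. Section 3.3 explains Cohort 2 partly by the wish to learn how treatment duration affects patients' own expenses, with rural travel singled out. Travel cost is paid at each visit, so it is directly tied to the number of fractions. FACIT-COST asks about attitudes and financial strain and records no dollar amounts, so the gap falls on the Cohort 2 form that collects patients' dollar figures.

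**Working it through.** The plan gives no figure to reproduce. The check is a trace of the form's routing, a comparison with the schedules, and a range for the possible extent.

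**1. Routing**

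| Situation of the patient | Answer | Sent to the cost items? |
|---|---|---|
| From home, daily | Yes | Yes |
| Friend or family home | No, second option | Yes, by instruction |
| Hotel or apartment | No, third option | Yes, by instruction |
| Health care facility | No, first option | No, by design |
| From home, not daily | No, no option fits | No |

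Two of the three no-options return to the cost items, one does not, and none fits the last row.

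**2. Does the last row occur?** The experimental schedule has a week between fractions and is never daily. For the control arm, the mean gap between k fractions spread over D days is D/(k − 1):

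| Fractions | D = 21 days | D = 14 days |
|---|---|---|
| 3 | 21/2 = 10.5 | 14/2 = 7.0 |
| 4 | 21/3 = 7.0 | 14/3 = 4.7 |
| 5 | 21/4 = 5.25 | 14/4 = 3.5 |

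The 21 days is the limit in section 6.1; the 14 days is an illustrative shorter course. Control patients can therefore also be treated weekly or otherwise non-daily, and the Background (section 3) describes the three-fraction regimen as given a week apart. Section 6.1 sets only an upper limit, so closer spacing is not excluded.

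**3. Possible extent (all inputs assumed).** Let h be the share of patients travelling from home, q the chance that a non-daily home traveller answers no and skips the block, and s the share of the control arm treated non-daily. The documents give none of these. Take h = 0.6 to 0.8 and q = 0.2 to 0.8.

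- Share with the block skipped in an arm treated wholly non-daily: h × q = 0.6 × 0.2 = 0.12 to 0.8 × 0.8 = 0.64. With 40 per arm this is 40 × 0.12 = 4.8 to 40 × 0.64 = 25.6, about 5 to 26 women. If every woman reads the question loosely and answers yes, q = 0 and nothing is lost.
- Excess in the experimental arm, if control patients on daily schedules answer yes: h × q × (1 − s).

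| s | Excess, percentage points |
|---|---|
| 1 | 0 |
| 0.5 | 6 to 32 |
| 0 | 12 to 64 |

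**4. What is lost and what is kept.** Lost: transport mode and the per-visit parking, shuttle, public-transport and taxi amounts. Kept: hours and distance (asked before the question), and accompaniment, child care and lost wages (outside the commuting block).

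**The case against.** The strongest reply is that this is a small wording gap in a form with several safeguards. Time and distance are collected from everyone. Zip codes are collected separately (section 8, note 7). An expense diary supports the survey (section 8, note 11; Appendix J), and section 12.2 has missing data queried with the sites. The data are exploratory and summarised without tests, and many women may read the question loosely and answer yes.

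Most of that stands, and it limits the consequence. It does not close the gap. The diary is only recommended, and the copy of the survey questions enclosed with it carries the same routing. Distance does not yield parking or fares. A site query may recover an amount, but only if the blank is recognised as an omission.

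Four stronger readings are tempting, and the documents do not support them:

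- **All no answers bypass the cost items.** They do not; the friend/family and hotel options return to them.
- **The loss is greater in the two-fraction arm.** No control scheme is specified as daily, and the mix of schemes is not stated. If all control patients are also treated non-daily (s = 1), the difference is zero.
- **Travel cost is recorded as zero.** A skipped item is blank. Nothing in the plan scores it as zero, so no distorted cost ratio between arms can be derived.
- **No financial objective uses the survey.** Section 2.2.2 does group it with diet and activity. However, section 2.2.1 speaks of reporting every individual measure, which could be read to include it.

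**Conclusion.** The point holds for one group: women in either arm who travelled from their own home on a non-daily schedule. Followed as written, the form does not direct them to the transport-mode and per-visit cost items, so those costs may be missing. This rests on the wording of Appendix I and the schedules in section 6.1, and needs no numerical assumption.

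The extent is unknown. The range of about 5 to 26 of 40 women is illustrative and depends wholly on the assumed shares; the true figure could be lower, including none. Whether missingness differs between arms cannot be settled from the documents.

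The consequence is incomplete descriptive cost data in an exploratory part of Cohort 2. The FACIT-COST primary endpoint and its planned confidence intervals are not affected. The correction is worth making because it is cheap, and amounts not asked for at the time may be hard to recover later.

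**What to change.** 1. In Appendix I, reword the question to: *Did you travel from your own home for your radiation treatments?* Those who answer no are then the women the three existing options describe. Alternatively, keep the question and add an option for patients who travelled from home but not daily, with the same instruction to return to the cost items. Update the copy enclosed with the Appendix J diary.
2. Flag forms completed under the current wording. A no answer with no place of stay ticked and an empty transport block identifies the likely cases for a site query.
3. State in section 10.2.5 that blank cost items are treated as missing, not as zero, and report the number missing by arm.
4. As a separate minor correction, list the survey in section 2.2 under the financial-toxicity objective instead of diet and physical activity.

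The cost is one reworded line on a form (or one added option), short edits to sections 2.2 and 10.2.5, and IRB review of the amendment under section 14.6. No change to sample size, schedule or primary analysis is needed.

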6.3 Duration of Therapy

Patients in the experimental arm should have treatment completed within two weeks of the first fraction given. Patients in the control arm should have treatment completed within three weeks of the first fraction given.

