8 STUDY CALENDAR

Examination	Screening ¹	Brachytherapy	Follow-up ⁶	Follow-up ⁶	Follow-up ⁶	Long term Follow-up ⁶
			1 month +/- 12 weeks	6 months +/- 12 weeks	12 months +/- 12 weeks	24 and 36 months +/- 12 weeks
Informed consent	X					
Medical history	X					
Eligibility criteria	X					
Vital signs	X		X	X	X	
Physical examination	X		X	X	X	
Pelvic exams	X		X	X	X	
WHO/ECOG performance status	X		X	X	X	
QLQ30 Questionnaire²		X	X	X	X	
EN24 Questionnaire²		X	X	X	X	
Collection of Cost Data⁴				X		
Collection of Distance Data⁷					X⁸	
Vaginal Cuff Brachytherapy³		X				
Adverse Event assessments		X	X	X	X	
Chart Review⁵						X
COHORT 2 Only						
COST-FACIT¹⁰			X			
Health Care Expense Survey¹¹		X	X			
NCI Diet History Questionnaire III (DHQ-3)⁹			X			
Physical Activity Questionnaire (ACT24)⁹			X			

1. All Pre-study/Screening procedures should be completed less than or equal to 12 weeks before study treatment.

2. Both the QLQ30 and EN24 questionnaires (appendix E and F) should be administered at baseline (prior to the first brachytherapy fraction) and at the 1 month, 6 month, and 12 month follow-up visits. See section 7.2.1 for guidance on participants experiencing severe emotional distress.
3. Subjects randomized to the control arm will undergo one of the three treatment options described in section 5 over no more than 3 weeks. Subjects randomized to the experimental arm will undergo the treatment described in section 5 over no more than 2 weeks. See Appendix D for treatment planning and dose reporting form.
4. Collection of cost data for analysis is described in section 9.2
5. The PI will continue to review patient medical charts at 24 and 36 months for disease reoccurrence at one of the following locations: vaginal, pelvic, or distant.
6. In person visits are preferred to allow for exams, so almost all visits will be done on site. If a patient is ill or cannot travel, questionnaires and history may be obtained via telemedicine. Missed exams will be considered deviations.
7. Patient's zip code and the location of the treatment facility will be collected and documented by the study staff.
8. If the information is not collected at the 12 month follow up visit, it will be collected at a subsequent time point or from patient's medical record.
9. Completion of the DHQ-3 and ACT24 is strongly encouraged, however, incompleteness will not result in a protocol deviation.

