10. See section 7.2.2 for guidance on participants experiencing severe emotional distress due to financial toxicities.
11. It is recommended that the Healthcare Expense diary be given to the participant prior to radiation to accurately track expenses throughout treatment. The diary should be collected from the patient at a follow-up visit.

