14.4.2 Serious Adverse Event (SAE)

Information about all serious adverse events will be collected and recorded.

A serious adverse event is an undesirable sign, symptom or medical condition which:

- Is fatal or life-threatening
- Results in persistent or significant disability/incapacity
- Is medically significant, i.e., defined as an event that jeopardizes the patient or may require medical or surgical intervention to prevent one of the outcomes listed above
- Causes congenital anomaly or birth defect
- Requires inpatient hospitalization or prolongation of existing hospitalization, unless hospitalization is for:
 - Routine treatment or monitoring of the studied indication, not associated with any deterioration in condition (procedures such as central line placements, paracentesis, pain control).
 - Elective or pre-planned treatment for a pre-existing condition that is unrelated to the indication under study and has not worsened since the start of study drug.

- Treatment on an emergency outpatient basis for an event not fulfilling any of the definitions of a SAE given above and not resulting in hospital admission.
- Social reasons and respite care in the absence of any deterioration in the patient's general condition.

SAE evaluation will begin after the first treatment and will continue until the first follow up visit, 28 days (+/- 14) after the completion of study treatment. If the patient is unable to attend the first follow up visit, the SAE reporting period will be extended to 56 days after the completion of study treatment.

Any death from any cause while a patient is receiving treatment on this protocol or up to 30 days after the last dose of protocol treatment, or any death which occurs more than 30 days after protocol treatment has ended but which is felt to be treatment related, must be reported.

Toxicities which fall within the definitions listed above must be reported as an SAE regardless if they are felt to be treatment related or not. Toxicities unrelated to treatment that do NOT fall within the definitions above, must simply be documented as AEs in the patient research chart.

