Appendix J - HEALTH CARE EXPENSE DIARY FOR SURVEY COMPLETION

Use this diary to record your health care-related expenses from the time you start radiation therapy until 6 to 10 weeks after you have completed radiation therapy. A copy of the survey questions is included with this diary for your reference.

Protocol name: Short Course Adjuvant Vaginal Brachytherapy in Early Endometrial Cancer Compared to Standard of Care

Version Date: 18JUN2025

Principal Investigator: [name]

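### The Cohort 2 expense survey counts lost work to 40 days after radiation but is scheduled at one month, and its diary runs 6 to 10 weeks, so coverage is incomplete at the nominal visit and varies between patients

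*Combined protocol and SAP*

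**What the plan says.** Appendix I places its work-loss items under a stated period: "From the 1st day of starting radiation, until 40 days after the completion of radiation". The items that follow include "Number of days the patient was unable to go to work at all", part-time days and the hours reduced on them, child care costs, and "Estimate wages lost due to radiation therapy".

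The Study Calendar (Section 8) marks the survey at brachytherapy and at the first follow-up, headed "1 month +/- 12 weeks". Section 2.2.2 also places it at one month after brachytherapy. The safety section (14.4.2) describes the first follow-up more narrowly, with serious adverse events collected "until the first follow up visit, 28 days (+/- 14) after the completion of study treatment".

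Appendix J, titled as a diary for completing the survey, asks the patient to record expenses from the start of radiation "until 6 to 10 weeks after you have completed radiation therapy". Calendar footnote 11 recommends giving out the diary before radiation and adds: "The diary should be collected from the patient at a follow-up visit". It does not say which visit.

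On treatment length, Section 6.1 gives the experimental arm two fractions one week apart, and Section 6.3 sets a two-week limit. For the other arm, Section 6.3 says: "Patients in the control arm should have treatment completed within three weeks of the first fraction given". No minimum duration is set for the control schedules.

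Section 2.2.1 plans to report and compare mean scores between the Cohort 2 arms. Section 10.2.5 limits the exploratory endpoints to descriptive tables without formal tests.

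**The concern.** Three periods that should fit together do not. The survey looks back over 40 days after radiation, the visit at which it is scheduled falls nominally before those 40 days are over, and the diary meant to support the answers is still running at that visit. No section says when the survey is final. Two patients with the same work history could report different totals because their forms came back on different days.

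Appendix I is the only instrument in the trial that counts lost workdays and asks for an amount of lost wages. Section 3.3 gives the effect of treatment duration on patients' own expenses as a reason for Cohort 2, and these figures are intended as baselines for later trials. Totals taken over unequal periods are hard to interpret even when they are only tabulated.

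There is also a smaller question of comparability. The counting period starts at the first fraction, so its length depends on how long treatment lasts, and the day counts are not restricted to absence caused by radiation.

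**Working it through.** The plan gives no figure of its own for this point, so the check is day arithmetic on the stated periods. Days are counted from completion of radiation unless stated otherwise.

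**1. Coverage at the one-month form.** Post-treatment days not yet elapsed = 40 − day of completion, if positive.
- Nominal visit, day 30: 40 − 30 = 10 days (10/40 = 25%).
- Nominal visit, day 28: 40 − 28 = 12 days (12/40 = 30%).
- Section 14.4.2 window, 28 ± 14, i.e. day 14 to 42: from 40 − 14 = 26 days missing down to none. Only a form completed on days 40 to 42 covers the whole period.
- Calendar window, 12 weeks = 84 days either side: the late bound is 28 + 84 = 112 to 30 + 84 = 114. The early bound falls before the end of treatment (30 − 84 = −54). Completion is allowed both well before and well after day 40.

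As a share of the whole counting period, a day-30 form misses 10/47 = 21% after a 7-day course and 10/61 = 16% after a 21-day course.

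**2. Diary against survey.** Six to ten weeks is day 42 to 70.
- Beyond the end of the survey period: 42 − 40 = 2 to 70 − 40 = 30 days.
- Still to run at a day-30 visit: 42 − 30 = 12 to 70 − 30 = 40 days.

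A completed diary therefore covers the survey period, but it cannot be complete at the nominal visit. The next scheduled visit is at six months.

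**3. Length of the counting period by arm.** Period = days from first to last fraction + 40.

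| Schedule | Span (days) | Period (days) |
|---|---|---|
| Experimental, one week apart (6.1) | 7 | 47 |
| Experimental, two-week limit (6.3) | 14 | 54 |
| Control, three weekly fractions (assumed spacing) | 14 | 54 |
| Control, three-week limit (6.3) | 21 | 61 |
| Control, five consecutive weekdays (assumed; not excluded by 6.1) | 4 | 44 |

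Control minus experimental ranges from 44 − 54 = −10 to 61 − 47 = +14 days. Limit against limit it is 61 − 54 = +7. Three weekly fractions against two a week apart also gives 54 − 47 = +7 (54/47 = 1.15). The medical delay of up to two weeks allowed in Section 7.1 can lengthen the period in either arm.

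**4. What unequal periods could do to the day counts.** Spurious difference = rate of unrelated absence × difference in period. The documents give no rate. Assuming 0.02 to 0.20 days per calendar day:
- +7 days: 0.14 to 1.4 days.
- +14 days: 0.28 to 2.8 days.
- −10 days: −0.2 to −2.0 days.

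These are illustrations, not estimates.

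**The case against.** The strongest reply is that nothing need be lost. The calendar window lets the form be completed after day 40, the diary may be collected at any follow-up visit, and a diary kept for at least 42 days contains everything the survey asks. This stands against saying that the data are truncated as a matter of course. It does not answer the point: the window permits late completion without requiring it, equally permits early completion, and sits beside a narrower description of the same visit in Section 14.4.2.

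A reader might also infer that the form favours the experimental arm even with no true effect. The documents do not support that, for four reasons.
- The visit and the 40 days are both counted from the end of radiation, so a form completed on a given day misses the same number of days in either arm.
- The control arm has an upper limit on duration but no minimum, so its counting period can equal or fall below the experimental one.
- The child care and wage items are confined to losses due to radiation. Only the day counts can pick up unrelated absence.
- Work missed because a course is longer is part of the duration effect that Section 2.2.1 sets out to explore.

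Comparing the ideal experimental schedule with the control limit (61/47 = 1.30) and reading it as 30% more lost days would further assume that all absence is unrelated to treatment and occurs at a constant rate.

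Nor is the whole survey affected. Parking, transport, lodging and hours per treatment are asked outside the 40-day heading, and several FACIT-COST items address expense and work. Appendix I already has a completion date.

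**Conclusion.** The inconsistency is real and follows from the documents alone: the survey period, its scheduled visit and the diary period cannot all be met at the nominal one-month visit, and the last 10 to 12 of the 40 post-treatment days are then unobserved. Across patients the shortfall can be anything from none to most of the period, depending on when the form is returned.

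The between-arm point is secondary and conditional. Unrelated absence can accrue longer in the control arm where its course is longer, as at the three-week limit or with assumed weekly spacing. Neither the direction in every patient nor the size can be established without the delivered schedules and an absence rate.

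Severity is minor. The survey is an exploratory, descriptive measure, and the Cohort 2 primary endpoint, FACIT-COST, uses a seven-day recall and is untouched.

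**What to change.** 1. State one post-treatment period and use it in both Appendix I and Appendix J.
2. Either finalise the survey at a contact on or after the day that period closes, by phone or mail if no visit falls there, or shorten the period so that it ends by the one-month form. Amend the calendar entry and footnote 11 to name that contact, and reconcile the timing of the first follow-up between Sections 8 and 14.4.2.
3. In the analysis, use the existing completion date and the treatment dates on the Appendix D form to derive observed days for each patient. Report lost days per observed day alongside totals, by arm.

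The cost is small: edits to two appendices and the calendar, plus either one remote contact per patient or a shorter recall period. Any forms already returned can be combined with later ones only through a per-day rate, which assumes that absence is spread evenly over the period.

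A fixed period counted from the first fraction would equalise total length, but it is a trade-off rather than a correction. With 61 days, a 7-day course leaves 61 − 7 = 54 post-treatment days and a 21-day course leaves 61 − 21 = 40. Keeping equal post-treatment time and reporting a rate is a defensible alternative.
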